
Formal follow-up assessments are planned at 1 and 3 months. The 3-month follow-up is designed to capture our primary outcome of tobacco abstinence. It is plausible that the effect of the BNI may be short lived and therefore we have scheduled an early initial follow-up (e.g., 30 days). To decrease respondent burden the 1 and 3 month assessments will be collected via telephone. Subjects self-reporting tobacco abstinence at 3 months will be asked to return to the ED to measure exhaled carbon monoxide, a validated measure of tobacco abstinence. In our prior ED study, we found that low-income subjects were easier to reach by phone earlier in the month rather than later, perhaps because of loss of cellphone service due to financial difficulties. Therefore, we will “front-load” our follow-up calls in the first half of each month.⁵⁵

Baseline Assessments

Baseline instruments have been selected for their ability to test the specific study aims, for brevity, and ease of administration. Demographic and locator information in all groups will be collected by face-to-face interview.

a. Demographic information: includes age, sex, racial/ethnic group, educational level and insurance status.

b. Exhaled carbon monoxide (CO). All patients will receive biochemical verification of smoking status, via point-of-care measurement of exhaled CO. Testing will be performed by a trained research associate with the Bedfont Micro+® breath CO monitor (Bedfont Scientific Ltd.) Calibration will be performed every 6 months, as recommended, by a research assistant. CO levels will be used to verify clinical equivalence of treatment groups at baseline. Consistent with standard practice, a cutoff of 10 ppm will indicate current smoking.⁵⁶

INSTRUMENT	Base-line	Month	
		1	3
BASELINE AND OUTCOME MEASURES			
Intake History/Patient Demographics	X		
Exhaled carbon monoxide level	X		X
PHQ-2 Depression Screen	X		
Treatment engagement		X	X
Causal attribution scales	X		
Wisconsin Predicting Patients' Relapse	X	X	X

Questionnaire			
Heaviness of Smoking Index	X	X	X
Rapid Alcohol Problem Screen	X		X
Rapid Drug Problem Screen	X		X
Self-report of tobacco use	X	X	X
PROCESS/IMPLEMENTATION MEASURES			
Treatment Service Review (TSR)		X	X

c. The Patient Health Questionnaire-2 (PHQ-2) will be used to assess depressive symptoms.⁵⁷ This 2-item scale, which rates the frequency and duration of depressive symptoms during the past two weeks, has shown excellent reliability and

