i. Rapid Drug Problems Screen (RDPS). The RDPS is a 4-item tool patterned after the RAPS.⁶⁴ It is designed specifically for detecting drug use within medical settings. It is a newer instrument and has less well-established test characteristics than the RAPS, but preliminary data for use in the ED setting are promising.⁶⁴ A "yes" response on any of the items places the participant in the "likely" group. For males, the RDPS has demonstrated good test characteristics when validated against ICD-10 and DSM-IV criteria for drug abuse or dependence, with a sensitivity of 93% and specificity of 96%. The validation study did not have enough subjects to adequately assess the RDPS' test characteristics among females.

Process measures

a. The Treatment Service Review (TSR),⁶⁵ a brief, structured interview, will be administered to collect information on the type and amount of services received by subjects. This includes ED visits, hospitalizations, primary medical care visits, and self-help sources of support (e.g. quitline, web services). The TSR will be supplemented with questions on the use of smoking cessation medications.

b. Adherence to the BNI manual: All BNIs will be audiotaped and reviewed by [name] and the RAs, to assess time with the patient, material reviewed, and proficiency of the provider at each session.

Outcome measures

a. Treatment engagement will be assessed by subject self-report, reports from Consumer Wellness Solutions, Inc. on QL use, and reports from ICFI International on texting engagement. Patients will be considered engaged in treatment if at 30-days after randomization the patient reports currently receiving care in a treatment program that addresses the patient's nicotine dependence.

b. Self-report tobacco use at 1 and 3 months. Several measures will be assessed, as recommended by an expert panel.⁶⁶ The primary endpoint is 7-day point prevalence abstinence; secondary endpoints are 30-day and continuous abstinence. A time-line follow-back (TLFB) technique^{67,68} will be used for all endpoints.

c. Exhaled carbon monoxide: will be collected in-person at baseline and in-person at 3 months, for subjects self-reporting abstinence. *In our prior study, 94% of self-reported abstainers returned for testing.*

d. Use of cessation medications and services. Quitline use, NRT use, use of other pharmacotherapies such as bupropion and varenicline will be assessed by self-report and fax reports from the CT quitline.

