12. Statistical Considerations: Describe the statistical analyses that support the study design. **Analytic strategy: overview.** Intervention components will be analyzed over three domains, as outlined in Figure 2. First, components will be assessed for clinical efficacy, using traditional measures such as biochemically verified tobacco abstinence. If clinically effective, components will then be analyzed for cost-effectiveness and feasibility/acceptability to providers and subjects. For the economic analysis, we will use standard approaches that assess quality-adjusted life years. For the qualitative assessments, we will interview research subjects to assess the feasibility and acceptability of the intervention components. Components that are clinically efficacious, cost-effective, and feasible and acceptable will be retained in the final package, which will be compared to a control condition in a follow-on randomized clinical trial. Analytic tactics are described in detail in the next few sections.

8. Biostatistical considerations. Primary Study Endpoints and Analyses. The primary efficacy endpoint for this study will be biochemically verified 7-day cessation rate at 3 months.⁶⁶ Tobacco use will be assessed by self-report and confirmatory biochemical testing with exhaled carbon monoxide. Patients who assert abstinence by phone interview will be asked to return to hospital for assessment of exhaled carbon monoxide.

Baseline comparability. The adequacy of the randomization will be assessed by comparing the distribution of baseline demographic and clinical characteristics among the intervention groups. Comparability for continuous variables will be examined graphically and by summary statistics,

and categorical variables by calculating frequency distributions. Data analyses will be conducted using SAS 9.3 (SAS Institute, Cary, NC).

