Analysis for Aim 1. The primary outcome, abstinence at 3 months, will be compared between the presence and absence of each component using logistic regression. Per convention, in the primary analysis missing abstinence data will be imputed as relapse. For this full-factorial design, the model will include main effects for each of the 4 components as well as all 2, 3 and 4-way interactions. The regression will also include baseline covariates: age, sex, race/ethnicity, and smoking characteristics. Main effects will be evaluated at the 0.05 significance level. Differences in proportions for the presence and absence of each component (i.e. main effects)

will be estimated along with 95% confidence intervals using the bootstrap method.⁷⁴ A p-value of 0.10 will be used as a guide to flag potentially important interactions which will be explored graphically with a particular emphasis on identifying substantial synergistic effects or qualitative (i.e. where the impact of one component changes direction depending on the presence or absence of another component) effect modification. Similar analyses will be performed at 1-month follow-up. Additionally, a logistic regression with parameters estimated by weighted Generalized Estimating Equations (GEE) will incorporate both 1 and 3-month outcome data without imputing non-responders as relapse.⁷⁵ This analysis weights for the probability of response and is valid under the assumption that missing data are missing at random (MAR). Secondary outcomes at 1 and 3 months will also be evaluated by a generalized linear model with weighted GEE.

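### Does the supplementary two-visit weighted GEE need respecifying because it names neither the abstinence measure at each visit nor a 3-month contrast?

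*Combined protocol and SAP*

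**What the plan says.** All references are to the combined protocol and SAP.

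- **Endpoint.** Biostatistical considerations, Primary Study Endpoints and Analyses: the "primary efficacy endpoint for this study will be biochemically verified 7-day cessation rate at 3 months".
- **Self-report measures.** Outcome measures, item b, covers self-reported tobacco use at 1 and 3 months: "The primary endpoint is 7-day point prevalence abstinence; secondary endpoints are 30-day and continuous abstinence".
- **CO.** Outcome measures, item c: exhaled CO "will be collected in-person at baseline and in-person at 3 months, for subjects self-reporting abstinence". The schedule table likewise shows none at month 1.
- **Mode and timing.** Measures: "To decrease respondent burden the 1 and 3 month assessments will be collected via telephone". The same section explains the early visit: "It is plausible that the effect of the BNI may be short lived and therefore we have scheduled an early initial follow-up".
- **Analysis.** Analysis for Aim 1 makes the primary analysis a 3-month logistic regression with missing abstinence counted as relapse. It then says "Similar analyses will be performed at 1-month follow-up", and adds a logistic model fitted by weighted GEE that "will incorporate both 1 and 3-month outcome data without imputing non-responders as relapse". The weights are for the probability of response, and validity is claimed under MAR.
- **Other missing-data work.** Plan for missing data adds pattern-mixture and selection models under MNAR.

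Nothing states which abstinence measure enters the GEE at month 3, or names a time term, a component-by-time term or a 3-month contrast.

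**The concern.** The GEE is the only analysis of abstinence in the plan that is stated to rest on MAR. A reader would want it to show whether counting non-responders as smokers drives the 3-month result. Two ways of filling in the missing detail would spoil that use.

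- **One common effect.** Suppose verified status is used at month 3, self-report at month 1, and each component has a single effect across visits. Its estimate is then an average over two times and two definitions. The plan itself expects the interview effect might fade. Month 1 also falls within the 6 weeks of NRT and the 6 to 8 weeks of texting, while month 3 falls after both.
- **Self-report throughout.** The GEE is then coherent, but it addresses a different endpoint from the CO-verified one.

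In either case a difference between the GEE and the primary result could come from timing or endpoint definition and not from missing data.

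**Working it through.** **1. The plan's planning rates.** Sample size and power calculations gives 4.9% without a component, a 5-point gain (so 9.9% with it), two-sided 0.05, 80% power and 860 in total. With mean rate 0.074 and pooled variance under the null:

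n per level = [1.960·√(2·0.074·0.926) + 0.842·√(0.049·0.951 + 0.099·0.901)]² / 0.05² = (0.7256 + 0.3101)² / 0.0025 ≈ 429.1, rounded up to 430.

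The total is 860, as stated. The 3-month odds ratio is (0.099/0.901)/(0.049/0.951) = 2.13.

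**2. How far a common effect can stray: pilot counts.** The texting pilot (Preliminary Studies, item 2) gives self-reported abstinence at both visits.

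- 1 month, 14/30 vs 3/30: OR = (14/16)/(3/27) = 7.88, difference 36.7 points.
- 3 months, 9/30 vs 4/30: OR = (9/21)/(4/26) = 2.79, difference 16.7 points.
- Fitting logit p = b0 + b1·treatment + b2·visit (independence working correlation): common OR 4.76, implied 3-month difference 24.0 points.
- Adding treatment × visit: 3-month OR 2.79, difference 16.7 points.

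**3. The same check at trial scale.** One component, complete data, equal numbers per level and visit. The 1-month self-report rates are assumed, since the documents give none for a single component.

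| 1 month, without/with (assumed) | 3 months, without/with | Common OR | Implied 3-month difference | 3-month OR with component × visit |
|---|---|---|---|---|
| 10% / 15% | 4.9% / 9.9% | 1.77 | 3.8 points | 2.13 |
| 10% / 20% | 4.9% / 9.9% | 2.21 | 5.2 points | 2.13 |
| 10% / 30% | 4.9% / 9.9% | 3.22 | 7.4 points | 2.13 |
| 10% / 15% | 4.9% / 4.9% | 1.38 | 1.5 points | 1.00 |
| 10% / 20% | 4.9% / 4.9% | 1.80 | 2.7 points | 1.00 |

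The last column does not move. With a component-by-visit term the month-3 rates are fitted by their own parameters, so the month-1 definition cannot leak into the month-3 contrast. An exchangeable working correlation does not alter this: with 30,000 per group and 10%/30% at month 1, the GEE month-3 OR and the raw month-3 OR were both 2.193.

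**4. Which readings the text allows.**

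- *Verified at month 3, one common effect:* distorted as in the fourth and fifth columns. The text does not prescribe this.
- *Self-report at both visits:* a sound analysis of a different endpoint. In the prior trial 66/774 = 8.5% were verified and, if the 97 claimants come from that same trial, 97/774 = 12.5% claimed abstinence.
- *Verified at month 3, self-report at month 1, component-by-visit terms:* the month-3 contrast addresses the CO-verified endpoint under the plan's MAR assumption.

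The third reading is as open as the others. It also fits a plan that names a 3-month primary endpoint and analyses month 1 separately.

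**5. Claimants who do not return for CO.** Taking the cited 92/97 return and 66/92 = 71.7% verified, expected claimants among 430 per level are 430·0.049/0.717 = 29.4 and 430·0.099/0.717 = 59.3. No-shows: (29.4 + 59.3)·5/97 = 4.6 people in 860. Leaving the 3-month claim out of the weights turns a 5.0-point difference into 4.8.

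**The case for a change.** The strongest case for a change is that the plan itself anticipates effects that vary by visit, and the pilot shows such a pattern (7.88 at 1 month, 2.79 at 3 months). If a component did nothing at month 3 but doubled self-reported abstinence at month 1 (10% to 20%), a common-effect GEE would reach p < 0.05 in 89 to 96% of simulated trials with 449 per level (1056 × 0.85 / 2). For 10% to 15% the figure is 36 to 49%. The 3-month contrast is significant in only 4 to 6% of the same trials. Adding the interaction would also not help if the GEE used self-report throughout, because the verified endpoint would then have no MAR analysis. The cost of a remedy is a few words in the SAP.

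What stands is the omission: the text does not fix the outcome or the contrast. The consequence does not follow from it. The large figures need an unstated common-effect model together with assumed 1-month rates, and at 10%/20% with the planned 3-month effect the distortion is 5.2 against 5.0 points. The pilot had 30 per arm and tested a package, and the sample size section expects single components to do less. The simulated percentages are not decision error rates either, because main effects are tested in the primary 3-month model. On the self-report reading, the verified endpoint still has relapse imputation and the MNAR models, so its sensitivity to missing data is not left unexamined.

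**Conclusion.** The gap is real but is one of detail, and no change to the plan is needed. No stated rule produces a wrong answer. The endpoint is defined at 3 months, the measures available at each visit are set out, and an analyst fitting two visits would ordinarily include visit-specific effects and report month 3. Done that way with verified status at month 3, the contrast recovers the 3-month odds ratio (2.13 at planning rates) whatever is recorded at month 1. The CO-return point concerns about 5 people in 860 and 0.2 of a percentage point. A second MAR analysis would be a preference, and the absence of CO at month 1 is already plain from the measures section.

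This rests on two things: the analysis being fitted with visit-specific effects, which the text permits but does not state, and the GEE remaining supplementary. The second is as written, since the primary logistic regression and the MNAR models stand apart from it and component selection does not refer to it. The exact equality in the working is for complete data; with missing responses it depends on the MAR assumption the plan already declares.

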Calculating C/E ratios: We will calculate ICERs in two passes. A naive first pass will array cost and regression-adjusted quit rate for each of the 16 MOST cells, ignoring if differences are statistically significant. This naive look will let us drop clearly dominated cells where higher cost is associated with a lower quit rate, as well as any cells that proved infeasible in the clinical setting or were unacceptable to staff. In a refined pass, we will define incremental component cost effectiveness as $\Delta C/\Delta E$, where ΔC is the cost a component adds and ΔE is the effectiveness associated with the component. This refined look at the remaining candidates will use two effectiveness measures, the 3-month quit rate and the simulated quality-adjusted life year (QALY) gain. A QALY is a standard measure of health-related quality of life, defined so that a year in perfect health is valued at 1.0 and death is valued at 0.0.⁷⁷ Even if one component costs more per quitter than another, it still may be worthwhile if it helps more smokers to quit at an acceptable cost per QALY gained. By estimating QALYs gained per quitter, we get a measure that lets us judge the cost of cessation gains relative to other smoking interventions, with a tentative ceiling of **\$5000** per QALY gained that we will refine in year 4 by updating our literature review on cessation interventions regularly used in medical settings.

The analysis will require estimates of the QALY losses and medical costs averted by smoking cessation. For QALY loss, the most recent estimates⁸¹⁻⁸³ are better than older estimates.^{84,85} For medical costs, we expect to use the latest update to CDC's SAMMEC model¹ which build from the methods pioneered by V. Miller.⁸⁶ We will inflate all cost savings to the same year's dollars as the program costs and compute present value of savings in future years at a 3% discount rate. To account for relapse, we will insert our chosen smoking costs and our observed quit rate pattern into the widely used BENESCO (benefits of smoking cessation on outcomes) Markov simulation model of cessation duration or a closely related model.^{78,79} These models stem from a 2002 World Health Organization model. The resulting estimates will let us answer the question, which efficacious ED-based interventions maximize quits while staying below the acceptable cost per QALY gained.

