To better inform our package choice, we will estimate 95% CIs around the ICERs. To estimate ratio variance, we will start with roughly estimated standard errors or distributional data for each number in the cost-effectiveness equation. We will use bootstrapping simulation

methods that form an empirical probability distribution.⁸⁷ To handle estimates with unknown variance, notably the discount rate, we will conduct sensitivity analyses. The sensitivity analyses examine if different input assumptions would change package selection.

10. Qualitative analysis. The final analytic strategy is a mixed methods analysis of those components found to be clinically efficacious. The goal of this analysis is to ensure that those components are considered feasible, practical, and acceptable by the *patients* who we wish to use the package in real-world settings. Intervention components scoring well in Likert assessments and found feasible and acceptable in interviews with subjects (that are also clinically efficacious and cost-effective) will be retained to study in the future randomized trial.

As we did previously, we will conduct phone interviews with study subjects to assess their views of the components, alone and in combination. Unlike our earlier qualitative work, which focused on the texting component only, we will assess subjects' view of all components in the factorial design: texting, BNI, QL, and NRT. *As before*, Likert-type questions will be included. We will make sure to sample individuals who were randomized to each of these as a single intervention. We will also sample individuals who were in arms where we identify important 2-way or 3-way interactions of efficacy.

We will use a grounded theory approach, in which explanatory theories will emerge from inspection of themes derived from coded transcripts.^{88,89} All interviews will be audiotaped and professionally transcribed. Interviews will be coded by [name] and study personnel with experience in coding. Subjects will be interviewed until thematic saturation is reached. We anticipate this will mean 25-30 subjects. [name] will use ATLAS.ti (ATLAS.ti GmbH).

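### Bootstrap intervals on the ICER can mislead for cost-saving or barely significant components; incremental net benefit from the same draws would not

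*Combined protocol and SAP*

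**What the plan says.** Section V, item 12, part 9 (Economic analysis) of the combined protocol and SAP defines the incremental ratio as ΔC/ΔE, "where ΔC is the cost a component adds and ΔE is the effectiveness associated with the component". It uses two effectiveness measures: "the 3-month quit rate and the simulated quality-adjusted life year (QALY) gain". On savings it says "The analysis will require estimates of the QALY losses and medical costs averted by smoking cessation", and that the analysts will "compute present value of savings in future years at a 3% discount rate". A tentative ceiling of $5,000 per QALY is given, to be refined in year 4. No ceiling per quit is given.

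On uncertainty the plan says "To better inform our package choice, we will estimate 95% CIs around the ICERs". It continues: "To estimate ratio variance, we will start with roughly estimated standard errors or distributional data for each number in the cost-effectiveness equation", followed by bootstrap simulation "methods that form an empirical probability distribution".

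The overview of the analytic strategy in item 12 sends only clinically effective components on to the cost-effectiveness step. Nothing in the document mentions net benefit, an acceptability curve, or how to order or report draws with ΔE ≤ 0 or ΔC < 0.

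**The concern.** A ratio loses its ordering once either part can change sign. A draw that costs more and does harm gives a negative ratio, and so does a draw that saves money and helps. Even among draws that save money and help, the more negative ratio is not always the better result. An interval taken from the sorted ratios can therefore place the worst outcomes next to the best ones.

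Averaging over all participants does not remove this. If averted costs enter ΔC, net cost can be negative for an efficacious component, and the cost table describes texting as having a small marginal cost. The intervals help decide which components go into the follow-on trial and bear on Hypothesis 2, that at least one intervention is cost-effective. An interval that looks wholly favourable when the data leave doubt would overstate the case for a component.

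**Working it through.** **Precision of ΔE.** The sample size section gives 4.9% abstinence without a component, a 5-point increase, two-sided 0.05 and 80% power. The pooled-variance formula for two proportions (4.9% v 9.9%) gives 429.1, rounded up to 430 per level, or 860 in total. This matches the plan. With 1056 enrolled, half at each level of a component, and missing outcomes counted as relapse, n = 528 per level. Then SE(ΔE) = √[p₀(1−p₀)/528 + p₁(1−p₁)/528].

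**How often ΔE ≤ 0.** At a true 5-point effect, 0.1% of draws; at 3 points, 2.3%; at 2 points, 8.4%. If a component must first reach p < 0.05 in the favourable direction, the share is at most about 2.5%.

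**When net cost is negative.** If savings are netted, ΔC = C − S·ΔE, with C the component cost per patient and S the averted cost per extra quitter. ΔC < 0 once S > C/ΔE. At 5 points this is 20/0.05 = $400 for an assumed $20 component and 150/0.05 = $3,000 for an assumed $150 component.

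**Why negative ratios do not rank.** Net benefit is NB = λ·ΔQALY − ΔC, with λ = $5,000.

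| ΔC | ΔQALY | ΔC/ΔQALY | NB |
|---|---|---|---|
| −$50 | 0.025 | −$2,000 | $175 |
| −$50 | 0.05 | −$1,000 | $300 |
| +$50 | −0.05 | −$1,000 | −$300 |

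The second row is better than the first but has the less negative ratio. The third is harmful and costly, yet has the same ratio as the second.

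**Illustrations.** The documents give no component cost, QALYs per quitter or averted cost, so these are assumptions. QALYs and savings per quitter are held fixed.

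*A. ΔE = 3.2 points, C = $100, 1.5 QALYs and $5,000 averted per quitter.* SE = 0.01514 and z = 2.11. ΔC = 100 − 5,000 × 0.032 = −$60; ΔQALY = 1.5 × 0.032 = 0.048; ICER = −60/0.048 = −$1,250. NB = 5,000 × 0.048 + 60 = $300. Each unit of ΔE is worth 5,000 × 1.5 + 5,000 = $12,500, so SE(NB) = 12,500 × 0.01514 = $189. The 95% CI is 300 ± 1.96 × 189, or −$71 to $671, and P(NB > 0) = 0.94. The simulated percentile ICER interval is about −$2,360 to $8,000.

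*B. 26/528 v 42/528, C = $20 (SD 10%), 1 QALY and $5,000 averted per quitter.* ΔE = 16/528 = 0.0303 and z = 2.01. ΔC = 20 − 151.5 = −$131.5; ICER = −$4,340; NB = 151.5 + 131.5 = $283. In 200,000 draws the percentile ICER interval is −$4,725 to −$473, negative throughout. The NB interval is −$18 to $585. About 2.6% of draws have ΔE ≤ 0. The share of draws with a ratio below $5,000 is 0.987, against P(NB > 0) = 0.968. The gap arises because harmful, costly draws also have ratios below the ceiling.

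*C. Planned 5-point effect, C = $100, 1.5 QALYs per quitter.* With no averted cost, the ICER interval is about $815 to $3,536 and NB $40 to $511. With $5,000 averted, they are about −$2,516 to $201 and $133 to $917. Both summaries favour the component in each case.

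**The case against.** The strongest reply is that the plan already limits exposure. A reader might infer from the first pass over the 16 cells, done "ignoring if differences are statistically significant", that near-zero effects feed the ratio intervals used for package choice. The documents do not support that. The first pass drops dominated or infeasible cells, and the overview of the analytic strategy admits only clinically effective components to the cost-effectiveness step. A component at 2.5 points (z = 1.69) would not pass at the 0.05 level. The economic overview does speak of each component, which leaves some ambiguity, but the gate largely closes this route.

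Two other stronger readings also fail. The plan does not say that savings are netted into ΔC; that is an inference from the discussion of averted costs and discounted savings, and it would not naturally apply to the per-quit ratio. Nor does the plan specify percentile limits. Quadrant-aware ordering or Fieller limits would lessen the problem, but neither is stated.

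It is also fair that the two summaries often agree. In illustration A the ICER interval spans $5,000 and the NB interval spans zero, so both read as uncertain. In B the conflict is narrow: with one more quitter (43 rather than 42, z = 2.12) the NB interval becomes $1 to $604. The intervals only inform a choice that also rests on efficacy, the ceiling and acceptability.

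What remains is that negative net cost does not depend on the efficacy gate, and the plan has no rule for handling it.

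**Conclusion.** The concern holds in a limited form and is a low-cost improvement; it is not a flaw that threatens the trial. Interval estimates of the raw ratio can mislead for components with negative net cost and for those that only just reach significance. At the planned 5-point effect the conclusion is the same either way.

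The size rests on assumed costs of $20 to $150 per patient, 1 to 1.5 QALYs per quitter and up to $5,000 averted per quitter, on savings being netted into ΔC, and on simple percentile limits. Fixing the QALY and savings inputs leaves their own uncertainty out of the intervals shown.

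**What to change.** State whether averted medical costs enter ΔC. Keep the ICER point estimates and the existing selection rule (most quits subject to the cost-per-QALY limit). From the same draws, report each component's incremental net benefit on the QALY scale with its 95% CI, and the probability that it exceeds zero, at $5,000 and over a range of ceilings because that figure is tentative. Use these in place of the ICER interval when judging uncertainty for package choice.

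Resample trial-measured cost and effect jointly by participant, and draw the external QALY and averted-cost inputs from their own distributions.

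The cost is a few lines of code and no new data. There is a small downside: net benefit depends on a ceiling. The plan already uses one for QALYs but gives none for the per-quit ratio, so that measure would need its own ceiling or remain a point estimate.
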